Appendix A. Protocol Deviations

The number and percentage of subjects who reported at least one of the following protocol deviation categories will be provided.

- Subject entered into the study even though s/he did not satisfy entry criteria.
- Subject developed withdrawal criteria during the study and was not withdrawn.
- Subject received wrong treatment or incorrect dose of study.
- Subject took prohibited concomitant medication.

Appendix B. Definition of Adverse Events of Special Interest

AESI will be identified by the following CMQ, SMQ, and other search criteria:

Table B-1. AESI for Upadacitinib with SMQs/CMQs/PTs Searches

AESI	Type of MedDRA Query	Broad or Narrow Search	SMQ/CMQ Search Criteria
Serious Infections	CMQ		"Infections" – Subset for SAEs
Opportunistic Infections excluding Tuberculosis and Herpes Zoster	CMQ		"Opportunistic Infection excluding tuberculosis and herpes zoster"
Active Tuberculosis	CMQ		"Active Tuberculosis"
Herpes Zoster	CMQ		"Herpes Zoster"
Adjudicated Gastrointestinal Perforations	Based on adjudicated results (per GI Perforation charter) of events identified by the "Gastrointestinal Perforation" SMQ Narrow search		
Anemia	CMQ		"Non-Hemolytic and Non-Aplastic Anemias"
Neutropenia	CMQ		"Hematological Toxicity – Neutropenia"
Lymphopenia	CMQ		"Hematological Toxicity – Lymphopenia"
Creatine Phosphokinase (CPK) Elevations	PT		Search for the PT of "Blood creatine phosphokinase increased."
Hepatic Disorders	SMQ	Narrow	"Drug Related Hepatic Disorders – Comprehensive Search"
Renal Dysfunction	SMQ	Narrow	"Acute Renal Failure"
Malignancies (all types)	SMQ		"Malignant tumors"

AESI	Type of MedDRA Query	Broad or Narrow Search	SMQ/CMQ Search Criteria
Malignancies excluding non-melanoma skin cancer (NMSC)	SMQ	Narrow	Malignant Tumors SMQ (Narrow) removing NMSC output
NMSC	SMQ	Narrow	Skin Malignant tumors (Narrow SMQ) removing Melanoma CMQ
Lymphoma	SMQ		"Malignant Lymphomas"
Adjudicated Cardiovascular Events	Output from CAC ^a		
MACE*			
Cardiovascular Death			
Non-fatal Myocardial Infarction			
Non-fatal Stroke			
Other Cardiovascular Events			
Undetermined/Unknown Cause of Death			
Adjudicated Thrombotic Events	Output from CAC ^a		
VTE**			
Deep Vein Thrombosis			
Pulmonary Embolism			
Other Venous Thrombosis			
Arterial Thromboembolic Events (non-cardiac, non-neurologic)			

CAC = Cardiovascular Adjudication Committee; CMQ = company MedDRA query; PT = preferred term; SMQ = standard MedDRA query

* MACE: Major Adverse Cardiovascular Events, defined as cardiovascular death, non-fatal myocardial infarction and non-fatal stroke.

** VTE: Venous thromboembolic events, defined as deep vein thrombosis (DVT) and pulmonary embolism (PE) (fatal and non-fatal).

a. Reviewed and adjudicated by an independent Cardiovascular Adjudication Committee in a blinded manner.

Table B-2. Exposure-Adjusted Rate Analyses for AESI

Analysis	EAER*	EAIR**	Cumulative Inc. Prop.
AESI (Section 10.2.6)			
Serious Infections	X	X	X
Opportunistic Infections excluding Tuberculosis and Herpes Zoster	X	X	X
Active Tuberculosis	X	X	X
Herpes Zoster	X	X	X
Adjudicated Gastrointestinal Perforations	X	X	
Anemia	X	X	X
Neutropenia	X	X	X
Lymphopenia	X	X	X
Creatine Phosphokinase (CPK) Elevations	X	X	
Hepatic Disorders	X	X	
Renal Dysfunction	X	X	
Malignancies		X	X
Malignancies excluding Non-Melanoma Skin Cancer (NMSC)		X	X
NMSC		X	X
Lymphoma		X	X
Adjudicated Cardiovascular Events		X	X
Adjudicated Thrombotic Events		X	X

* EAER: Exposure-adjusted event rate.

** EAIR: Exposure-adjusted incidence rate.

Appendix C. Potentially Clinically Important Criteria for Safety Endpoints

The criteria for Potentially Clinically Important (PCI) criteria for vital sign findings are described in Table C-1.

Table C-1. Criteria for Potentially Clinically Important Vital Sign Values

Vital Sign	Category	Criteria for Potential Clinically Significant Vital Signs
Systolic blood pressure	Low	Value \leq 90 mmHg and decrease \geq 20 mmHg from Baseline
	High	Value \geq 160 mmHg and increase \geq 20 mmHg from Baseline
Diastolic blood pressure	Low	Value \leq 50 mmHg and decrease \geq 10 mmHg from Baseline
	High	Value \geq 100 mmHg and increase \geq 10 mmHg from Baseline
Pulse	Low	Value \leq 50 bpm and decrease \geq 15 bpm from Baseline
	High	Value \geq 120 bpm and increase \geq 15 bpm from Baseline
Weight	High	> 7% increase from baseline
	Low	> 7% decrease from baseline

Appendix D. Crohn's Disease Activity Index (CDAI)

The Crohn's Disease Activity Index (CDAI) is a composite instrument that includes patient symptoms evaluated over 7 days (abdominal pain, stool frequency and general well-being), as well as physical and laboratory findings. These items are scored individually, weighted, and do not contribute equally to the overall score. The CDAI is derived from summing up the weighted individual scores of eight items as outlined below:

			Factor	Subtotal
1. Number of liquid or very soft stools (Record the frequency per day)	$\frac{_}{_} + \frac{_}{_} + \frac{_}{_} + \frac{_}{_} + \frac{_}{_} + \frac{_}{_} + \frac{_}{_} = \frac{_}{_}$ Days: 1 2 3 4 5 6 7 Sum	×	2	
2. Abdominal pain rating: 0 = none, 1 = mild, 2 = moderate, 3 = severe	$\frac{_}{_} + \frac{_}{_} + \frac{_}{_} + \frac{_}{_} + \frac{_}{_} + \frac{_}{_} + \frac{_}{_} = \frac{_}{_}$ Days: 1 2 3 4 5 6 7 Sum	×	5	
3. General well-being: 0 = generally well, 1 = slightly underpar, 2 = poor, 3 = very poor, 4 = terrible	$\frac{_}{_} + \frac{_}{_} + \frac{_}{_} + \frac{_}{_} + \frac{_}{_} + \frac{_}{_} + \frac{_}{_} = \frac{_}{_}$ Days: 1 2 3 4 5 6 7 Sum	×	7	
4. Number of 6 listed categories the subject now has Check all items that apply:  Arthritis/arthralgia  Iritis/uveitis  Erythema nodosum/pyoderma gangrenosum/aphthous stomatitis  Fissure, abscess and/or anal fistula (draining/non-draining)  Other cutaneous fistula (draining/non-draining) Fistula  Fever over 100°F (37.8°C) during past week	_____ _____ Record "0" if no categories checked	×	20	
5. Taking Lomotil/Imodium/ Loperamide/opiates for diarrhea 0 = no, 1 = yes	_____	×	30	
6. Abdominal mass 0 = none, 2 = questionable, 5 = defined	_____	×	10	
7. Hematocrit: ____.	Male: (47 – hematocrit) = Female: (42 – hematocrit) = Subtotal If hematocrit > normal, enter "0"	×	6	
8. Body weight: ____ (kg) Standard weight: ____ (kg)	$100 \times [1 - (\text{Body wt}/\text{Standard wt})] =$ Percent below standard weight: _____ If body wt > std. wt, enter "0"	×	1	
			Total	

Higher CDAI scores indicate more severe disease. For the calculation of CDAI and components (daily stool frequency, abdominal pain score and general well-being) at each visit, the following rules will be applied:

1. Identify the visit date with CDAI components that are collected, and set it as the CDAI calculation date.
2. Calculate the subtotal scores from the component 1-3 (liquid or very soft stool frequency, abdominal pain score and general well-being) as follows:
 - a. "14-4 approach"
 - i. Select the diary data from 14 days prior to the CDAI calculation date, and set the data from the 4 days (the day prior to, on the day of and two days after the endoscopy date) to missing;
 - ii. Take non-missing diary data from 7 most recent days from step i. If there are multiple entries on the same day for the eDiary component, use the worst result (larger number);
 - iii. If there are non-missing diary data from 7 days, the subtotal score is calculated as the sum of the 7-day scores, and multiplying the factor for the corresponding component as listed in the table above;
 - iv. If there are non-missing diary data from less than 7 days but greater than 3 days (4, 5, 6 days), the subtotal score is calculated as average of the dairy data and times 7, and multiplying the factor for the corresponding component as listed in the table above;
 - v. If there are only less than 4 days of non-missing diary data available, the subtotal score will be set to missing.
 - b. "9-2 approach"
 - i. Select the diary data from 9 days prior to the CDAI calculation date, and set the data from the 2 days (the day prior to, and on the day of the endoscopy date) to missing;
 - ii. Take non-missing diary data from 7 most recent days from step i. If there are multiple entries on the same day for the eDiary component, use the worst result (larger number);

- iii. If there are non-missing diary data from 7 days, the subtotal score is calculated as the sum of the 7-day scores, and multiplying the factor for the corresponding component as listed in the table above;
 - iv. If there are non-missing diary data from less than 7 days but greater than 3 days (4, 5, 6 days) OR from 3 consecutive days, the subtotal score is calculated as average of the dairy data and times 7, and multiplying the factor for the corresponding component as listed in the table above;
 - v. If there are non-missing diary data from 3 non-consecutive days OR less than 3 days of non-missing diary data available, the subtotal score will be set to missing.
- c. Average daily SF/AP will be determined in the same way as described above to derive PROs-related endpoints (for example, clinical remission per PROs);
 - d. The "14-4 approach" will be used to calculated CDAI, average daily SF/AP at each CDAI date. Sensitivity analyses which are based on "9-2 approach" to calculate CDAI and SF/AP will be performed on primary endpoints (Clinical Remission per CDAI at Week 12, Clinical Remission per PROs at Week 12).
3. Subtotal scores for components 4-6 (Number of 6 listed categories, usage of Lomotil/Imodium/Loperamide/opiates for diarrhea and abdominal mass) will be determined using the data collected on the CDAI calculation date and the corresponding formula in the table above;
4. Subtotal score for component 7 (Hematocrit) is calculated as follows:
- a. Identify the Hematocrit (%) value form the same visit as the CDAI calculation date, use the Hematocrit that is closest to the CDAI calculation date;
 - b. Hematocrit values obtained from previous visits can be used.
 - c. The subtotal score for Hematocrit is calculated using the formula in the table above. If Hematocrit value is greater or equal to 47% for male subjects (greater or equal to 42% for female subjects), the subtotal score is set to 0.

5. Subtotal score for component 8 (percentage below standard weight) is calculated as follows:
 - a. Standard weight is calculated based on height obtained at screening, sex and study protocol Appendix H;
 - b. Body weight is based on the measurement obtained on the CDAI calculation data, or previous visits if the measurement is missing.
 - c. The subtotal score for percentage below standard weight is calculated using the formula in the table above.
6. CDAI score is calculated as the sum of subtotal scores of 8 components, and the total CDAI score will be rounded to 1 decimal. If any of the subtotal scores are missing, the CDAI score will be missing.

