#### *Instructions to calculate CDAI*

- To answer **questions one (1) through three (3)**, entries from the 7 days prior to the visit should be used as recorded by the subject from the diary.
- Diary entries should not be included in the 7 days evaluated prior to the visit if:  
(1) the day the subject received medication for bowel preparation prior to

endoscopy, (2) the day the subject underwent an endoscopy, and (3) 2 days following the endoscopy. Diary entries, up to 14 days prior to the visit, will be used accordingly in order to provide the most recent data for 7 days prior to the respective study visit. The 7 days do not need to be consecutive.

- In **question four (4)**, for the section regarding presence of anal fistulas and other fistulas, all fistulas detectable on physical examination (draining and non-draining) should be captured on the CDAI and calculated into the CDAI score.
- The evaluation for fever should include all the days that are taken into account for the calculation of the CDAI.
- When completing **question five (5)** ("Taking Lomotil/Imodium/Loperamide/opiates for diarrhea, 0 = no, 1 = yes") on the CDAI, "no" should be answered if a subject is taking an opiate(s) solely for pain. The use of these medications takes into account only the day of the scheduled visit and is only assessing their use as anti-diarrheals.
- For **question seven (7)**, Hct results from central laboratory will be used for the CDAI calculation. If the Hct value contains more than one decimal point, the rounding will be allowed to the tenths decimal (e.g., Hct value 33.44 will be captured as 33.4, Hct value of 33.45 will be captured as 33.5). The Hct values either prior to completing the calculation or at the subtotal box 7 of the CDAI should not be rounded to a whole number.
- For **question eight (8)**, the height obtained at Screening should be used when selecting the standard weight in [Appendix H](#), and this standard weight should be used for calculating every CDAI throughout subject participation in the study.
- Standard height is calculated by using the height obtained at Screening (without shoes) adding 1 inch or 2.5 cm.

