## **5.5 Treatments**

### **5.5.1 Treatments Administered**

Study drug will be taken orally QD, beginning on Day 1 (Baseline), and should be taken at approximately the same time each day. The study drug can be taken with or without food. Subjects will continue their stable background CD therapy, if allowed per protocol. AbbVie will not supply any background CD therapy taken during the course of the study.

Study drug may be shipped from the study site directly to the study subject's home if all of the following criteria are met:

- Direct-to-patient (DTP) shipment of study drug is allowed by local regulations and the relevant ethics committee.
- Subject agrees to have the study drug shipped directly to their home.
- Shipments may also include other study supplies (e.g., paper copies of PROs, urine pregnancy tests). Instructions will be provided by AbbVie as to how a study site can initiate a DTP shipment using Marken, a global vendor selected by AbbVie to provide this service when necessary. Shipments of study drugs from the study site to a subject's home will be appropriately temperature controlled (qualified shipper or temperature monitoring) within the labeled storage conditions. Signature is required upon delivery; due to pandemic-

related social distancing, this may be provided by the courier after delivery. Documentation of the shipment is to be retained by the clinical site.

- AbbVie will not receive subject identifying information related to these shipments as the site will work directly with the courier.

The study site is responsible for meeting IRB/IEC reporting requirements related to DTP shipments of study drug and for obtaining consent to provide delivery information to the courier and documenting this consent in source documents.

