Subject Diary Review w,#		X	X	X	X	X	X	X	X	X	X	
Optional biologic drug level x,=	X											
Optional Pharmacogenetic y,=		X										
Optional Epigenetic y,=		X		X		X			X	X		
Optional Serum and Plasma y,=		X		X		X			X	X		
Optional mRNA y,=		X		X		X			X	X		
Optional Stool Proteomic y,z,=		X		X		X						
Optional Stool Microbiota y,z,=		X		X		X						
Optional Intestinal Biopsy aa,=	X					X			X	X		

CDAI = Crohn's Disease Activity Index; CSS = Crohn's Symptoms Severity Questionnaire; ECG = electrocardiogram; EQ-5D-5L = European Quality of Life 5 Dimensions 5 Levels; FACIT-F = Functional Assessment of Chronic Illness Therapy-Fatigue; FCP = fecal calprotectin; hs-CRP = high-sensitivity C-reactive protein; IBDQ = Inflammatory Bowel Disease Questionnaire; PGIC = Patient Global Impression of Change; PGI-S = Patient Global Impression of Severity; SES-CD = Simplified Endoscopic Score for Crohn's disease; SF-36 = Short Form-36; PD = premature discontinuation; WPAI = Work Productivity and Activity Impairment Questionnaire

- a. The Screening Period will be a minimum of 8 days but no more than 35 days prior to Baseline Visit. Baseline Visit date will serve as the reference for all subsequent visits. A ± 3-day window is permitted around scheduled study visits.
- b. Visits to retest a lab will not be considered an unscheduled visit. Unscheduled visits according to this table are for purposes when the subject is coming in for a visit for evaluation and assessment.

- c. Update inclusion/exclusion, prior and concomitant therapy, and medical/surgical history information to assure subject eligibility. All subjects need to have their average daily very soft or liquid SF and average daily AP score calculated and meeting eligibility criteria before randomization at Baseline.

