3.2 Secondary Endpoints

The ranked secondary endpoints for EU/EMA regulatory purposes are as follows:

Group 1A_E:

1. Achievement of clinical remission per CDAI at Week 12
2. Achievement of clinical remission per PROs at Week 4
3. Achievement of endoscopic remission at Week 12
4. Discontinuation of corticosteroid use for CD and achievement of clinical remission per PROs at Week 12 (population: ITT subjects taking corticosteroids for CD at Baseline)

5. Change from Baseline in Functional Assessment of Chronic Illness Therapy-Fatigue (FACIT-F) total score at Week 12
6. Change from Baseline in Inflammatory Bowel Disease Questionnaire (IBDQ) total score at Week 12

Group 1B_E:

7. Achievement of CR-100 at Week 2
8. Achievement of CR-100 at Week 12
9. Occurrence of hospitalizations due to CD during Part 1
10. Achievement of resolution of extra-intestinal manifestations (EIMs) at Week 12 (population: ITT subjects with EIMs at Baseline) (see [Appendix G](#))

The ranked secondary endpoints for US/FDA regulatory purposes are as follows:

Group 1A_F:

1. Achievement of clinical remission per PROs at Week 12
2. Achievement of endoscopic remission at Week 12
3. Discontinuation of corticosteroid use for CD and achievement of clinical remission per CDAI at Week 12, in subjects taking corticosteroids for CD at Baseline
4. Change from Baseline in FACIT-F total score at Week 12
5. Change from Baseline in IBDQ total score at Week 12

Group 1B_F:

6. Achievement of CR-100 at Week 2
7. Achievement of CR-100 at Week 12
8. Achievement of clinical remission per CDAI at Week 4

9. Occurrence of hospitalizations due to CD during Part 1
10. Achievement of with resolution of EIMs at Week 12 (population: ITT subjects with EIMs at Baseline) (see [Appendix G](#))

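### The 14-day diary look-back has no cut at first dose, so an early Week 2 visit with a sparse diary can be scored partly on pre-treatment days; the effect on CR-100 at Week 2 is small and one date condition removes it

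*SAP*

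**What the plan says.** SAP Appendix D derives the three diary components of the CDAI by the 14-4 approach. Rule 2a(i) reads "Select the diary data from 14 days prior to the CDAI calculation date" and blanks four days around an endoscopy. Rule 2a(ii) continues: "Take non-missing diary data from 7 most recent days from step i". Rule 2a(iv) averages the data when 4 to 6 days are available. Rule 2a(v) gives the floor: "If there are only less than 4 days of non-missing diary data available, the subtotal score will be set to missing". Rule 2c extends the derivation to average daily stool frequency and abdominal pain, and rule 2d applies the 14-4 approach at each CDAI date.

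The protocol's instructions for calculating the CDAI say that "entries from the 7 days prior to the visit should be used". After listing the endoscopy days to leave out, they add: "Diary entries, up to 14 days prior to the visit, will be used accordingly". Neither document limits post-Baseline scores to days after the first dose, although SAP 9.1 does define Baseline by the first administration of study drug.

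On timing, Protocol Appendix C, footnote a, states: "A ± 3-day window is permitted around scheduled study visits". Protocol 5.5.1 makes Baseline Day 1 and the day of first dose. SAP 3.2 lists "Achievement of CR-100 at Week 2" seventh for EU/EMA (Group 1B_E) and sixth for US/FDA (Group 1B_F).

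**The concern.** A look-back as long as the time since first dose can reach back past that dose. At Week 2 it can, so symptoms recorded before treatment may be scored as a Week 2 outcome. The same diary entry can then count in both the Baseline and the Week 2 score, which shrinks the measured change.

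CR-100 requires a fall of at least 100 CDAI points, so one pre-dose day can decide a borderline subject. As a constructed example, take diary components worth 250 points at Baseline and 145 on treatment, with everything else unchanged. The on-treatment fall is 105, a responder. With one pre-dose day among the seven, the score is (6 × 145 + 250)/7 = 160 and the fall is 90, a non-responder. The example shows the mechanism, not how often it happens.

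At stake is a modest loss of sensitivity for an early-onset endpoint that is formally tested in both lists. Remission at Week 2 uses the same derivation but is not ranked.

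**Working it through.** **The plan's own figures.** There is none on this point: no diary-completion rate, no assumed CR-100 rate and no power for Week 2. The only power statement (at least 95% for each Week 12 co-primary endpoint, SAP 2.4) reproduces with Fisher's exact test at 99.4%, 99.6% and 98.7%. It is not in question here.

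**Step 1: calendar.** Baseline is Day 1, so Week 2 is Day 15 and the permitted range is Day 12 to 18. Counting back 14 days from each visit day:

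| Visit day | Day 1 onward | Before Day 1 | Entries from Day 1 onward that must be missing before a pre-dose day is used |
|---|---|---|---|
| 12 | 11 | 3 | at least 5 of 11 |
| 13 | 12 | 2 | at least 6 of 12 |
| 14 | 13 | 1 | at least 7 of 13 |
| 15 to 18 | 14 | 0 | not possible |

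The last column follows from rule 2a(ii): seven on-drug entries fill the score. With a complete diary, a Day 12 visit is scored on Days 5 to 11. Week 4 (Day 26 at the earliest) reaches back only to Day 12, so among the scheduled post-Baseline visits only Week 2 is exposed.

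**Step 2: chance that a pre-dose day is used.** Assume each day is missing independently with probability q. With m on-drug and r pre-dose days in the window,

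P = P(Bin(m, 1−q) ≤ 6) × (1 − q^r).

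For Day 12 and q = 0.2: 0.0504 × (1 − 0.008) = 0.0500.

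| q | Day 12 | Day 13 | Day 14 | Average, visits even over Day 12–18 | Expected out of 495 |
|---|---|---|---|---|---|
| 10% | 0.27% | 0.05% | 0.01% | 0.05% | 0.2 |
| 20% | 5.0% | 1.9% | 0.6% | 1.1% | 5 |
| 30% | 20.5% | 10.7% | 4.4% | 5.1% | 25 |

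The average is the sum over the three exposed days divided by 7; for q = 0.3, (20.5 + 10.7 + 4.4)/7 = 5.1%. The last column assumes all 495 have a Week 2 visit.

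**Step 3: the Day 1 entry.** SAP 9.5 shows that the diary's total-stool question covers roughly the preceding 24 hours. If the other items share that recall (an assumption), a Day 1 entry mostly describes time before the dose. Moving Day 1 to the pre-dose side gives 1.3%, 12.1% and 34.8% at a Day 12 visit for q = 10%, 20% and 30%. A Day 15 visit is then also touched. The averages over Day 12–18 become 0.2%, 2.8% and 10.0%.

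**Step 4: direction.** With 4 to 6 on-drug entries, a score exists with or without the pre-dose days, and adding them usually moves it towards Baseline. With 1 to 3 on-drug entries, pre-dose days can lift the count to 4 and create a score where a cut would leave it missing, hence a non-responder under NRI-C. The present rule can then only add a responder. At a Day 12 visit with Day 1 counted as on drug, the first situation has probability 5.0% (q = 20%) or 20.0% (q = 30%), the second 0.02% or 0.4%.

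**Step 5: effect on power.** Assume CR-100 rates of 20% and 33%, and, pessimistically, that affected upadacitinib subjects respond at the placebo rate. Power for 165 versus 330 at an unadjusted two-sided 0.05 is 86.9% with nobody affected, 86.3% with 1% affected, 85.0% with 3% and 79.5% with 10%.

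**The case against.** The strongest reply is that the seven-day selection already protects the score: an early visit alone brings in nothing, because the subject must also have missed about half of the on-drug diary. The protocol works against that, with daily completion, site review at every visit and reinforcement. The rule is the same in both arms, its net effect is attenuation, and Group 1B is tested only after both co-primary endpoints and all of Group 1A succeed. Nearly all of this stands, and it is why the point is minor.

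A reader might also infer that the SAP contradicts the protocol. It does not clearly do so. The protocol itself allows entries up to 14 days back and sets no cut at first dose. Tying that extension to the endoscopy exclusions is a plausible reading, since the sentence follows them directly and no endoscopy is scheduled at Week 2, but it is not stated.

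The reply does not remove the gap. Followed exactly, the rule uses pre-treatment entries whenever an early visit meets a sparse diary. No planned analysis would show it: the 9-2 approach would reach only Day 3 from a Day 12 visit, but it is confined to the Week 12 primary endpoints. Nor is the reach-back needed at Week 2, since 4 to 6 days are already accepted.

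**Conclusion.** The rule as written lacks a lower bound at first dose. For visits on Day 12 to 14 with a sparse diary, it scores pre-treatment days as a Week 2 outcome. This can slightly attenuate CR-100 at Week 2 in both lists.

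The size rests on assumptions the documents do not supply: the daily missing rate, independence of missing days and an even spread of visit days. Across 10% to 30% missingness, about 0.05% to 5.1% of Week 2 scores are touched, or 0.2% to 10.0% with Day 1 treated as pre-dose. Gaps that cluster within a subject would raise these shares. At 10% missingness or below the matter is negligible if Day 1 counts as on drug.

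Two stronger readings are tempting. One is that the rule dilutes CR-100 at Week 2 as a matter of course; rule 2a(ii) prevents that for any reasonably complete diary. The other is that the error always runs towards Baseline; the cases with 1 to 3 on-drug entries run the other way, and a single pre-dose day can be a mild one. Nothing here raises the false-positive risk or touches the Week 12 co-primary endpoints. This is a cheap improvement, not a threat to the trial's conclusions.

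**What to change.** Add one sentence to SAP Appendix D, rule 2a(i): *For post-Baseline visits only diary entries dated after the day of first dose of study drug are selected.* Leave rules 2a(ii) to 2a(v) unchanged, so that 4 to 6 remaining days are averaged and fewer than 4 give a missing score. Report, by arm, how many Week 2 scores the cut changes, including those that become missing. That count replaces the assumed missing rates above with the actual impact.

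The programming cost is one date condition. The analytic cost is that subjects left with fewer than 4 entries become missing and so count as non-responders under NRI-C. Because the wording also drops Day 1, a Day 12 visit has 10 eligible days, and the chance is P(Bin(10, 1−q) ≤ 3): about 0.09% at 20% daily missingness and 1.1% at 30%. Keeping Day 1 would give 0.02% and 0.4%, but would leave in an entry that may largely describe time before the first dose.

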#### **Diary Based**

The ePRO data (number of total and liquid or very soft stools, stool consistency per Bristol Stool Chart, use of medications used for endoscopy preparation, if an endoscopy was performed, AP, and general well-being) will be collected electronically via a handheld device into which the subject will record the required pieces of information on a daily basis. The electronic device will be programmed to allow data entry once per day.

All data entered on the device will be immediately stored to the device itself and manually/automatically uploaded to a central server administrated by CRF Health. The investigational site staff will be able to access all uploaded subject entered data via a password protected website, up until the generation, receipt and confirmation of the study archive.

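### SAP Appendix D drops diary days by a fixed offset from the endoscopy date and ignores the recorded bowel-preparation days, so an earlier preparation day can enter the EU and US clinical co-primary scores; the expected effect is small

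*SAP*

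**What the plan says.** Protocol Section 5.3.1.1 (Instructions to calculate CDAI) keeps certain days out of the 7-day score. The first is "the day the subject received medication for bowel preparation prior to" endoscopy; the others are listed as "2) the day the subject underwent an endoscopy, and (3) 2 days following the endoscopy". The gaps are filled from older entries: "Diary entries, up to 14 days prior to the visit, will be used accordingly". Protocol Section 10.3 (Diary Based) lists among the daily items "use of medications used for endoscopy preparation, if an endoscopy was performed", so a preparation day can be identified from the data.

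SAP Appendix D, rule 2a(i) (the 14-4 approach), uses the endoscopy date alone: "set the data from the 4 days (the day prior to, on the day of and two days after the endoscopy date) to missing". Rule 2b(i) (the 9-2 approach) does the same over a shorter span: "set the data from the 2 days (the day prior to, and on the day of the endoscopy date) to missing". Neither rule refers to the preparation item. Rule 2c extends the derivation beyond the CDAI: "Average daily SF/AP will be determined in the same way as described above to derive PROs-related endpoints". Rule 2d makes 14-4 the main rule and 9-2 the sensitivity analysis. The SAP version history (Section 13.0) does not explain the departure from the protocol.

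**The concern.** Stools, pain and poor well-being caused by a laxative are not disease activity, and the protocol removes them for that day. The SAP substitutes the calendar day before the endoscopy for the recorded preparation day. The substitution is exact for a one-day preparation on the eve of a completed procedure. It fails in two situations:

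- Preparation was also taken two days before the endoscopy.
- Preparation was taken for a procedure that was then postponed or aborted and left no endoscopy date to count from. The protocol foresees rescheduling in its Endoscopy section, although its diary instructions do not clearly cover this case.

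A laxative day left in the score can push a subject above the stool-frequency limit for remission per PROs (EU/EMA) or to 150 or more on the CDAI (US/FDA). The planned sensitivity analysis also works by offset from the endoscopy date, so agreement between 14-4 and 9-2 would give no reassurance on this point. Endoscopic response is unaffected.

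**Working it through.** **Plan's own figure.** SAP Section 2.4 assumes 330 and 165 subjects, Fisher's exact test and two-sided 0.05, and claims at least 95% power. Exact enumeration gives 99.4% for PRO remission (29% vs 12%) and 99.6% for CDAI remission (40% vs 20%). The claim is reproduced and is not in dispute.

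**Which days are scored.** Count days back from the visit. Let the endoscopy be *e* days before it, with *e* from 0 to 7 (the Week 12 window in the protocol's Endoscopy section), and assume a complete diary. The 14-4 rule drops days *e*+1, *e*, *e*−1 and *e*−2; the 9-2 rule drops *e*+1 and *e*. Each then takes the 7 most recent remaining days. A preparation day two days before the endoscopy is day *e*+2.

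| *e* | Scored under 14-4 | Scored under 9-2 | Day *e*+2 |
|---|---|---|---|
| 0 | 2–8 | 2–8 | 2 |
| 1 | 3–9 | 3–9 | 3 |
| 2 | 4–10 | 1, 4–9 | 4 |
| 3 | 5–11 | 1–2, 5–9 | 5 |
| 4 | 1, 6–11 | 1–3, 6–9 | 6 |
| 5 | 1–2, 7–11 | 1–4, 7–9 | 7 |
| 6 | 1–3, 8–11 | 1–5, 8–9 | 8 |
| 7 | 1–4, 9–11 | 1–6, 9 | 9 |

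Day *e*+2 is scored in 8 of 8 timings under both rules. Excluding recorded preparation days removes it every time.

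**Effect on PRO remission.** The limit is an average of 2.8, so 7 × 2.8 = 19.6 and a weekly total of 20 fails. If the other six days average *m*, the retained day must reach 20 − 6*m* stools:

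- *m* = 2.0: 8 stools, since (12 + 8)/7 = 2.86
- *m* = 2.5: 5 stools, since (15 + 5)/7 = 2.86
- *m* = 1.5: 11 stools, since (9 + 11)/7 = 2.86

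**Effect on the CDAI.** The daily weights are 2 per liquid or very soft stool, 5 per pain grade and 7 per well-being grade (Protocol Appendix I). Ten extra stools with pain and well-being each one grade worse add 10 × 2 + 5 + 7 = 32 points. Remission requires a score below 150, so it is lost only when the true score is at least 150 − 32 = 118.

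**How many subjects.** Expected remitters at the planned rates:

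- PRO: 0.29 × 330 + 0.12 × 165 = 95.7 + 19.8 = 115.5, about 116
- CDAI: 0.40 × 330 + 0.20 × 165 = 132 + 33 = 165

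The share with preparation outside the day before endoscopy is not in the documents. At an assumed 2% to 5%, the exposed remitters number 2.3 to 5.8 (PRO) and 3.3 to 8.3 (CDAI). Only those close enough to a threshold would be misclassified.

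**Effect on the comparison.** If a share *f* of true remitters is lost equally in both arms, the difference is multiplied by 1 − *f*. Even if every exposed remitter were lost at *f* = 5%, the PRO difference would fall from 17 to 17 × 0.95 = 16.2 points and the CDAI difference from 20 to 19.0. Power would be 99.1% and 99.3%. At *f* = 20%, far beyond the assumed range, it would be 97.2% and 97.5%.

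**The case against.** The best defence is that the SAP simply puts the protocol rule into operation. The protocol speaks of one preparation day, tied to an endoscopy: 1 preparation day + 1 endoscopy day + 2 days after = 4, which is the SAP's count. No preparation regimen is given, so multi-day preparation is at most an ambiguity in the protocol. This limits the point but does not remove it. The protocol's exclusion follows from medication having been received, and the SAP never consults that record.

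Four stronger readings are tempting, and the documents do not support them.

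- **That the protocol excludes every preparation day, with or without an endoscopy.** Its wording presupposes an endoscopy. Covering an aborted procedure is a sensible extension and should be labelled as one.
- **That Baseline scores are inflated, making CR-100 and the conditions relative to Baseline easier to meet.** The 7-day window expressly exempts the screening endoscopy, which may be up to 45 days before Baseline, and Baseline must wait for the central reading. In the same enumeration, a preparation day two days before endoscopy enters the 14-4 score only if the endoscopy was 9 days or fewer before the visit. Any such error also precedes randomization, so it is balanced between arms in expectation.
- **That 2% to 5% of 495, or 10 to 25 subjects, would be misclassified.** That would be the number exposed under an assumed rate. At Week 12 only would-be remitters can be lost, and only near a threshold.
- **That the trial's conclusion is at risk.** Week 12 errors create false failures in either arm. If they are similar in both, the difference shrinks and the drug is not favoured.

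**Conclusion.** The mismatch between protocol and SAP is real, reaches the clinical co-primary for each regulator, and cannot be detected by the 9-2 analysis. It bites at Week 12 when preparation was also taken two days before the endoscopy, or for a procedure that left no endoscopy date. Baseline is affected only if the screening endoscopy falls inside the look-back.

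The size is small: at an assumed 2% to 5%, a handful of exposed remitters per endpoint, fewer of them misclassified, and a slight dilution of the treatment difference. This rests on the planned response rates, complete diaries, similar preparation patterns in both arms, and a frequency the documents do not give. It is a cheap improvement in the accuracy of the estimates and in fidelity to the protocol.

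**What to change.** In SAP Appendix D, rules 2a(i) and 2b(i), also set to missing every diary day with recorded use of endoscopy-preparation medication. Keep the existing offset days around each endoscopy date, then take the 7 most recent remaining days as now. State that, for preparation not followed by an endoscopy, this goes beyond the protocol's literal wording. If the offset rule is retained, say why and add a sensitivity analysis that uses the diary record.

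The cost is one line of text and programming on an item already collected. Under 14-4, with a complete diary and one extra day removed, 14 − 4 − 1 = 9 candidate days remain, so 7 are available and no score is lost. Under 9-2, 9 − 2 − 1 = 6 can remain, so some subjects would be scored on 6 days, which rule 2b(iv) allows. With other missing entries or repeated preparation, a subject may be scored on fewer days, or fall below the minimum and count as a non-responder under NRI-C (SAP Section 9.2.1). The number of subjects affected in this way should be reported.
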